6.7 Other Safety Considerations

Any significant worsening noted during interim or final physical examinations, electrocardiogram, x-ray filming, any other potential safety assessment required or not required by protocol should also be recorded as a nonserious or serious AE, as appropriate, and reported accordingly.

Second primary malignancies (SPMs) will be collected throughout the study for subjects treated with pomalidomide and includes assessments during survival follow-up. All SPMs that occur during the screening period and within 100 days of discontinuation of dosing will be reported as an SAE regardless of relationship to study drug. Additionally, any SPM that occurs after this timeframe and considered related to study drug will be reported as an SAE. All other SPMs will be collected and reported on a separate CRF page.

7 DATA MONITORING COMMITTEE AND OTHER EXTERNAL COMMITTEES

Not applicable.

8 STATISTICAL CONSIDERATIONS

[REDACTED]

[REDACTED]

[REDACTED]

[REDACTED]

[REDACTED]

8.2 Populations for Analyses

- All Enrolled Subjects: All subjects who sign informed consent form and were registered in IVRS.
- All Treated Subjects: All subjects who receive at least one dose of nivolumab and/or daratumumab.
- Response Evaluable Subjects: All treated subjects with measurable disease at baseline and one of the following: 1) at least one on-treatment efficacy assessment, 2) clinical progression, or 3) death.
- Pharmacokinetic (PK) Subjects: All subjects who receive at least one dose of study medication and have available serum concentration data.
- Biomarker Subjects: All subjects who receive at least one dose of study medication and have available biomarker data
- Immunogenicity Subjects: All subjects who receive at least one dose of study medication and have available ADA data.

8.3 Endpoints

8.3.1 Primary Endpoint(s)

8.3.1.1 Safety

The primary objective relates to evaluate the safety and tolerability of the nivolumab and daratumumab combination therapy in subjects with relapsed/refractory MM. This objective will be measured by the following endpoints:

- Number and percent of subjects that experience drug-related grade 3-4 AEs occurring up to 100 days after the last dose of study drug. [Time Frame - On a continuous basis up to 100 days after the last dose of study drug];
- Number and percent of subjects that experience drug-related grade 3-4 SAEs occurring up to 100 days after the last dose of study drug. [Time Frame - On a continuous basis up to 100 days after the last dose of study drug];
- Number and percent of subjects with clinical laboratory abnormalities by worst toxicity grade by NCI CTCAE version 4.0 (as assessed at the planned times listed in [Section 5.1](#)). (Time Frame - On a continuous basis up to 100 days after the last dose of study drug).

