The primary objective is to characterize the safety and tolerability of nivolumab and daratumumab. The primary objective will be measured by:

- Number and percent of subjects that experience drug-related grade 3-4 AEs occurring up to 100 days after the last dose of study drug. [Time Frame - On a continuous basis up to 100 days after the last dose of study drug];
- Number and percent of subjects that experience drug-related grade 3-4 SAEs occurring up to 100 days after the last dose of study drug. [Time Frame - On a continuous basis up to 100 days after the last dose of study drug];
- Number and percent of subjects with clinical laboratory abnormalities by worst toxicity grade by NCI CTCAE version 4.0 (as assessed at the planned times listed in Section 5.1). [Time Frame - On a continuous basis up to 100 days after the last dose of study drug].

Efficacy: Minimal Residual Disease (MRD) negativity status, objective response rate (ORR), duration of response (DOR), progression free survival (PFS), and overall survival (OS) for all treated subjects.

Both cytometry and molecular MRD from bone marrow aspirate will be evaluated. The time point for MRD negativity status for MM subjects in the nivolumab/daratumumab cohorts is a dichotomized variable for quantifiable MRD detection.

Pharmacokinetics: Nivolumab serum concentrations at the end of a dosing interval (C_{min}) and end of study drug infusion (Ce_{inf}) will be derived from serum concentration versus time data.

Immunogenicity: The frequency of nivolumab baseline ADA positive subjects and frequency of ADA positive subjects will be provided.

Biomarker: Additional exploratory biomarker studies will be performed as described in [Section 5.7](#).

Analyses:

Safety Analyses: All recorded adverse events will be listed and tabulated by system organ class, preferred term, treatment, and coded according to the most current version of MedDRA. The incidence of adverse events will be reviewed for potential significance and clinical importance. Vital signs and clinical laboratory test results will be listed and summarized by treatment. Any significant physical examination findings and results of clinical laboratory tests will be listed. ECG results will be evaluated by the investigator and abnormalities, if present, will be listed.

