3.1.1 Stopping Rules

3.1.1.1 Stopping Rules for Toxicity in the ND Arm

The ND arm will be stopped if any of the following safety events are observed:

- Grade \geq 3 nivolumab immune-related adverse events: \geq 10% occurrence in the first 50% of treated patients
- Grade 5 adverse events, excluding those due to disease progression, cumulative rate: \geq 20% occurrence in the first 50% of treated patients.

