6.1 Serious Adverse Events

A *Serious Adverse Event (SAE)* is any untoward medical occurrence that at any dose:

- results in death
- is life-threatening (defined as an event in which the subject was at risk of death at the time of the event; it does not refer to an event which hypothetically might have caused death if it were more severe)
- requires inpatient hospitalization or causes prolongation of existing hospitalization (see **NOTE** below)
- results in persistent or significant disability/incapacity
- is a congenital anomaly/birth defect
- is an important medical event (defined as a medical event(s) that may not be immediately life-threatening or result in death or hospitalization but, based upon appropriate medical and scientific judgment, may jeopardize the subject or may require intervention [eg, medical, surgical] to prevent one of the other serious outcomes listed in the definition above.) Examples of such events include, but are not limited to, intensive treatment in an emergency room or at home for allergic bronchospasm; blood dyscrasias or convulsions that do not result in hospitalization.) Potential drug induced liver injury (DILI) is also considered an important medical event. (See [Section 6.6](#) for the definition of potential DILI.)

Suspected transmission of an infectious agent (eg, pathogenic or nonpathogenic) via the study drug is an SAE.

Although pregnancy, overdose, cancer, and potential drug induced liver injury (DILI) are not always serious by regulatory definition, these events must be handled as SAEs. (See [Section 6.1.1](#) for reporting pregnancies.)

NOTE:

The following hospitalizations are not considered SAEs in BMS clinical studies:

- a visit to the emergency room or other hospital department < 24 hours, that does not result in admission (unless considered an important medical or life-threatening event)
- elective surgery, planned prior to signing consent
- admissions as per protocol for a planned medical/surgical procedure
- routine health assessment requiring admission for baseline/trending of health status (eg, routine colonoscopy)
- medical/surgical admission other than to remedy ill health and planned prior to entry into the study. Appropriate documentation is required in these cases

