#### 4 ENDPOINTS

##### 4.1 Primary

The primary objective to characterize the safety and tolerability of nivolumab monotherapy and combination therapy will be measured by the following endpoints:

- Number and percent of subjects that experience drug-related grade 3-4 AEs occurring up to 100 days after the last dose of study drug. [Time Frame - On a continuous basis up to 100 days after the last dose of study drug];
- Number and percent of subjects that experience drug-related grade 3-4 SAEs occurring up to 100 days after the last dose of study drug. [Time Frame - On a continuous basis up to 100 days after the last dose of study drug];
- Number and percent of subjects with clinical laboratory abnormalities by worst toxicity grade by NCI CTCAE version 4.0. [Time Frame - On a continuous basis up to 100 days after the last dose of study drug].

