### **7.6.1 Death**

See CORE Safety SAP.

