## 8.3 Multiple Measurements

### Laboratory Measures

For tabulations of changes from baseline the following will be used, in a hierarchical sequence, to select the post-treatment measurement included in the analysis (if a criterion does not apply it would be skipped in the sequence):

- If multiple laboratory measurements are obtained within the same scheduled time frame, then the measurement obtained on the time closest to the target time/day will be used;
- If more than one value meets the above criterion, then the measurement obtained on the earlier time will be used;
- If both local and central laboratory values qualify as baseline according to the above criterion, the central laboratory value will be used as the baseline value;
- If more than one value meets the above criterion, then the average value will be used.

For tabulations by CTC grade and summarized by worst toxicity grade, if multiple laboratory measurements are obtained within a analysis period (post-baseline), then the worst measurement within the analysis period, respectively, will be used.

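### Both event-based primary tolerability endpoints stop at Grade 4, so a nivolumab/daratumumab patient whose only severe drug-related event is fatal is counted in neither

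*Protocol*

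**What the plan says.** Protocol Section 8.3.1.1 lists three primary endpoints for tolerability of nivolumab plus daratumumab. Two count events: "Number and percent of subjects that experience drug-related grade 3-4 AEs occurring up to 100 days after the last dose of study drug" and "Number and percent of subjects that experience drug-related grade 3-4 SAEs occurring up to 100 days after the last dose of study drug". The third is "Number and percent of subjects with clinical laboratory abnormalities by worst toxicity grade by NCI CTCAE version 4.0". The synopsis (Endpoints, Safety) lists the same three.

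SAP Section 4.1 repeats them for all cohorts together: "The primary objective to characterize the safety and tolerability of nivolumab monotherapy and combination therapy will be measured by the following endpoints".

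Elsewhere the protocol treats fatal events as toxicity. The first criterion for a serious adverse event in Section 6.1 is that it "results in death". The ND stopping rules in Section 3.1.1.1 use Grade 3 or higher immune-related events, with no upper grade limit, and separately "Grade 5 adverse events, excluding those due to disease progression".

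For deaths, SAP Section 7.6.1 says only "See CORE Safety SAP". Sections 7.6.2 (serious events) and 7.6.5 (adverse events) make the same referral. Outside the laboratory endpoint itself, the one worst-grade rule is in SAP Section 8.3, and it too concerns laboratory values: "For tabulations by CTC grade and summarized by worst toxicity grade, if multiple laboratory measurements are obtained".

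**The concern.** A toxicity endpoint should not improve when an event gets worse. Here a drug-related event recorded as Grade 4 puts the patient in the numerator. The same event recorded only as Grade 5 leaves the patient out of the adverse event count, and out of the serious event count too, even though death makes an event serious by definition. Such a patient may still appear in the laboratory endpoint, but not because of the fatal event.

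The percentage by arm is the primary result. The synopsis says Cohort B is not powered for hypothesis testing, so no test sits behind it. A reader who takes that percentage as the severe drug-related toxicity rate would be reading a rate with the worst outcome removed, and would have to add in deaths reported elsewhere to recover the full rate.

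**Working it through.** **1. Which patients are affected.** Apply the endpoint text to each pattern of drug-related records:

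| Drug-related records | Counted in the two event endpoints? |
|---|---|
| Grade 3 or 4 only | Yes (serious-event count only if serious) |
| A Grade 3 or 4 event, plus a separate Grade 5 event | Yes, through the Grade 3 or 4 event |
| One event that worsens from Grade 3 or 4 to Grade 5 | Cannot be settled: no worst-grade or any-grade rule is stated for adverse events |
| Grade 5 only | No |

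The defect is certain for the last row and open for the third.

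**2. Size per patient.** The synopsis plans about 60 treated subjects in Cohort B, randomized 2:1, which gives 40 ND and 20 D.

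- ND: 1/40 = 2.5 percentage points per omitted patient.
- D: 1/20 = 5 percentage points.
- Example in ND: 8/40 = 20.0% becomes 7/40 = 17.5% with one omitted, or 6/40 = 15.0% with two.

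**3. The plan's own figures.** The synopsis (Sample Size) and SAP Section 5 give binomial chances of seeing few or many toxicities. With P(X ≤ k) = Σ C(n,i) pⁱ(1−p)ⁿ⁻ⁱ for i = 0 to k:

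| n | Quantity | Computed | Stated |
|---|---|---|---|
| 20 | P(X ≤ 1), p = 0.20 | 6.92% | 7% |
| 20 | P(X ≥ 2), p = 0.05 | 26.42% | 26% |
| 40 | P(X ≤ 3), p = 0.20 | 2.85% | 3% |
| 40 | P(X ≥ 4), p = 0.05 | 13.81% | 14% |

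All four reproduce and are not in dispute.

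**4. Illustration under an assumed rate.** Let q be the share of patients whose only severe drug-related record is Grade 5. The documents give no value, so a range is shown. The chance that at least one of 40 ND patients is omitted is 1 − (1 − q)⁴⁰. If the true drug-related Grade 3-5 rate is 20% (one of the plan's two example rates), the counted rate is 0.20 − q:

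| q | At least one of 40 omitted | Counted rate | P(0-3 counted in 40) |
|---|---|---|---|
| 0 | 0 | 20% | 2.8% |
| 1% | 33% | 19% | 4.0% |
| 2.5% | 64% | 17.5% | 6.3% |
| 5% | 87% | 15% | 13.0% |

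The last column borrows the plan's toxicity calculation. The plan does not define which toxicities that calculation covers and attaches no decision to the count.

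**5. Does the ND stopping rule fill the gap?** The Grade 5 rule acts at 20% or more in the first 50% of treated patients. If that means 20 ND patients, 0.20 × 20 = 4 events are needed, so 3/20 = 15% would not reach it. The chance of fewer than 4 in 20 is 98.4% at a true Grade 5 rate of 5%, and 86.7% at 10%. The rule covers one arm and part of its patients, and counts Grade 5 events whether or not drug-related, apart from those due to progression. It monitors safety; it does not put anyone into the endpoint.

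**The case against.** The strongest reply is that this is a deliberate and consistent convention. The synopsis, protocol body and SAP agree, and the other cohorts of the study use the same Grade 3-4 definition. On this view severe non-fatal toxicity and death are separate outcomes, each with its own place. Fatal events are collected as serious events to 100 days after dosing, tabulated with all adverse events (Protocol Section 8.4.3), given a Death section in the SAP, and included in overall survival. All of that is correct, and nothing here says deaths go unreported. But no passage carries them into the two primary percentages.

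The affected group may also be small. The endpoints count subjects who experience a Grade 3-4 event, not those whose worst grade is 3-4, and Protocol Section 6.1.1 requires a follow-up report when a serious event changes in intensity. A patient who passes through Grade 3 or 4 before death may therefore be counted. That reading is reasonable but not stated, and it does not help a patient with Grade 5 alone.

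The Core Safety SAP is not among the documents and may show Grade 5 beside Grade 3-4 by arm. If so, the reader's inconvenience shrinks. The defined numerator does not change, because SAP Section 4.1 sets it without reference to that document.

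Finally, the assumed Grade 5 rates have no source in the plan, and the chance of at least one omission does not measure distortion. Both points stand: only the per-patient effect follows from the planned arm sizes.

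**Conclusion.** The concern holds, and should be fixed. As written, both event-based primary endpoints exclude a patient whose only severe drug-related record is Grade 5, so a fatal event gives a lower primary toxicity rate than the same event at Grade 4. The firm size is 2.5 points per such patient in ND and 5 points in D, assuming 40 and 20 treated. The probabilities in the illustration rest on assumed Grade-5-only rates of 1% to 5%, and on a 20% overall rate taken from the plan's example. The consequence is for how the descriptive primary result reads. Confidence is high on the endpoint wording. How far the Core Safety SAP tables would offset it in reporting cannot be judged from these documents.

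**What to change.** For the nivolumab/daratumumab cohorts only, define the two endpoints in the synopsis, Protocol Section 8.3.1.1 and SAP Section 4.1 as the number and percent of subjects with drug-related Grade 3-5 adverse events and drug-related Grade 3-5 serious adverse events, each subject counted once if the worst grade is 3 or higher. Show Grade 3-4 and Grade 5 (drug-related deaths) as sub-rows by arm. The once-per-subject rule also settles the event that worsens to Grade 5. In SAP Section 4.1, make this a separate line so that the endpoints of the monotherapy, ipilimumab and lirilumab cohorts stay as they are. The stopping rules are not touched.

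The cost is a wording change in three places and one more grade level in descriptive tables, with no new data. The protocol part is a revision that needs ethics committee review under Section 9.1.1. Because the study is open-label, the date and reason for the change should be recorded; the change can only leave the reported rate equal or raise it. The headline rate will no longer match the Grade 3-4 definition of the other cohorts, but the Grade 3-4 sub-row keeps that comparison. A supplementary Grade 5 row alone would supply the information but leave the primary percentage as it is.

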The planned sample size for Cohort B (ND, D) will be approximately 60 treated subjects, randomized in a 2:1 ratio in favor of the ND arm.

This is a Phase 1/2 study and the sample size in Cohort B is not powered for statistical hypothesis testing but is designed to evaluate both safety profile and clinical benefit of nivolumab with daratumumab.

If the true toxicities incidence rate in a cohort is 20% then with 20 patients in D cohort, there is 7% chance of observing 0 - 1 toxicities (false negative rate). If the true toxicities incidence rate in a cohort is 5% rather than 20%, then there is 26% chance that there will be at least 2 toxicities in 20 subjects (false positive rate). If the true toxicities incidence rate in a cohort is 20% then with 40 patients there is 3% chance of observing 0 - 3 toxicities (false negative rate). If the true toxicities incidence rate in a cohort is 5% rather than 20%, then there is 14% chance that there will be at least 4 toxicities in 40 subjects (false positive rate).

In 2 daratumumab monotherapy studies in relapsed/refractory MM patients, including a Phase 1/2 dose escalation study (GEN501)ⁱ in patients with at least 2 lines of prior therapy and a Phase 2 study (SIRIUS)ⁱⁱ in patients with at least 3 lines of prior therapy, the ORR were 36% and 29.2% respectively.

In two combination studies in relapsed/refractory MM patients with at least 2 lines of prior therapy, including a Phase 1b study of daratumumab in combination with pomalidomide and dexamethasoneⁱⁱⁱ and a Phase 1 dose-escalation study of pembrolizumab in combination with lenalidomide and dexamethasone,^{iv} the ORR were 60%.

Table 8.1-1 summarizes the 95% exact CI for the target ORRs ranging from 30% to 80% with sample size of 20 or 40 in a cohort. At observed ORR \geq 55% with 20 subjects, the lower bound of the 95% CI is 31.5%. At observed ORR \geq 77.5% with 40 subjects, the lower bound of the 95% CI is 61.5%.

Table 8.1-2 summarizes the 95% exact CI for the target MRD-target negativity rates ranging from 10% to 30% with sample size of 20 or 40 in a cohort. At observed MRD-target negativity rates \geq 30% with 20 subjects and observed MRD-target negativity rates \geq 20% with 40 subjects, the lower bound of the 95% CI are 11.9% and 9.1% respectively compares favorably to historical MRD-target negativity rate of 8% in recurrent pretreated relapsed or refractory MM.

Endpoints:

Safety:

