3 INVESTIGATIONAL PLAN

3.1 Study Design and Duration

This is a Phase 1/2, open-label, multicenter, study of nivolumab, a fully human monoclonal IgG4 antibody targeting the PD-1 membrane receptor on T cells.

NIVOLUMAB/DARATUMUMAB COHORTS

Combination cohorts will evaluate the combination of nivolumab and daratumumab in relapsed/refractory MM patients.

Per Revised Protocol 14, Cohort A is closed to enrollment. Patients who are already on treatment in this cohort will continue to receive study treatment as long as they derive clinical benefit and do not meet the protocol defined criteria for discontinuation ([Section 4.1.5](#)). See [Figure 3.1-1](#).

Cohort B (ND, D) has been added to the study and is open to enrollment. See [Figure 3.1-2](#).

The study will consist of Screening (up to 28 days), Treatment (until disease progression), and Follow-up.

Figure 3.1-1: Study Design for Cohort A (ND ± Pd) Cohort A is closed for enrollment per Revised Protocol 14

[figure not shown]
[figure not shown]

Figure 3.1-2: Study Design for Cohort B (ND and D) Cohort B is open for enrollment per Revised Protocol 14.

* Split dosing is available for Cycle 1 Day 1. See [Section 4.1.1.2](#).

Dosing schematics for the nivolumab/daratumumab cohorts are provided in [Appendix 6](#).

Approximately 60 eligible MM subjects will be enrolled in Cohort B (ND and D) and will be randomized in a 2:1 ratio in favor of the ND regimen. Subjects will continue treatment as long as the subject has clinical benefit from the treatment and does not meet criteria for treatment discontinuation.

All AE data will be monitored on an ongoing basis for safety. Stopping rules for toxicity in the nivolumab-daratumumab arm are specified in [Section 3.1.1.1](#).

For assessment of MRD by molecular and cytometry approaches to detect disease in the bone marrow, all MM subjects will require bone marrow aspirates at the time points described in [Table 5.1-6](#).

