### **7.4.1 Study Therapy**

For nivolumab, ipilimumab, lirilumab, daratumumab, pomalidomide and dexamethasone, the following parameters will be listed and summarized.

- Number of doses
- Duration of therapy
- Cumulative dose per subject
- Dose intensity per subject (/week)
- Relative dose intensity per subject

Cumulative dose (mg/kg) is defined as: the sum over the duration of the study of all delivered doses (mg/kg) per subject.

Dose intensity per subject (/week) is calculated as the cumulative dose (mg/kg) divided by the duration of therapy (weeks).

Relative dose intensity is defined as dose intensity divided by planned dose per week (relative dose (%) = dose intensity / planned dose per week) \* 100).

Duration of therapy (weeks) is defined as: (last dose date - first dose date + 1)/7.

A listing of study drug administered will be provided. Duration of therapy, cumulative dose, dose intensity and relative dose intensity of relative study drugs will be listed. A listing of study medication by batch (or vial) number will be provided.

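### The two primary AE percentages in Cohort B are taken over a window that grows with time on treatment, so unequal exposure in ND and D can shift the side-by-side rates at equal monthly risk

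*Protocol*

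**What the plan says.** Protocol 8.3.1.1 defines the first primary endpoint as "Number and percent of subjects that experience drug-related grade 3-4 AEs occurring up to 100 days after the last dose of study drug". The second is the same for SAEs, and the third covers laboratory abnormalities by worst grade. The stated time frame is "On a continuous basis up to 100 days after the last dose of study drug". SAP 4.1 repeats all three.

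The length of treatment is open. Protocol 3.1 says "The study will consist of Screening (up to 28 days), Treatment (until disease progression), and Follow-up", and for Cohort B "Subjects will continue treatment as long as the subject has clinical benefit from the treatment and does not meet criteria for treatment discontinuation". The rule is the same for ND and D.

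The synopsis plans "approximately 60 treated subjects, randomized in a 2:1 ratio in favor of the ND arm", tabulates adverse events by treatment, and says that "the sample size in Cohort B is not powered for statistical hypothesis testing". Its toxicity figures, repeated in SAP Section 5, use a single incidence of 20% or 5% with no time dimension.

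Protocol 8.4.2 sets the final analysis once all treated subjects have at least 3 months of follow-up. Protocol 8.5.1 sets the Cohort B interim at 3 months for half of each arm.

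SAP 7.4.1 does summarise exposure ("Duration of therapy (weeks) is defined as: (last dose date - first dose date + 1)/7"), but the supplied text does not link it to AE rates. AE methods in SAP 7.6.1 to 7.6.13 are referred to a Core Safety SAP that is not among the documents.

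**The concern.** A crude percentage over a window of this kind mixes two quantities: the risk per month, and the number of months in which an event could be seen. The second depends on how long disease control lasts and how well treatment is tolerated, and adding nivolumab may change both. D is the only concurrent reference for ND, so readers will set the two percentages next to each other. Part of any gap may then reflect length of observation and not tolerability.

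A second effect acts on both arms. Three months is about 91 days, less than the 100-day tail. A subject at minimum follow-up cannot have completed the window even after a single dose, yet stays in the denominator and counts as event-free if nothing has happened so far. Randomisation should balance calendar follow-up, so this mainly makes the absolute rates too low.

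What is at stake is how the primary tolerability result is read. Type I error is not involved.

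**Working it through.** **The plan's own toxicity figures.** Exact binomial probabilities: 0–1 of 20 at 20%, 6.9% (plan 7%); at least 2 of 20 at 5%, 26.4% (plan 26%); 0–3 of 40 at 20%, 2.8% (plan 3%); at least 4 of 40 at 5%, 13.8% (plan 14%). All four reproduce. None involves time at risk.

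**Inputs.** From the documents: treatment to progression, a 100-day tail (w = 100/30.4375 = 3.285 months), and arms of about 40 and 20. Assumed, because the documents give none: the same constant first-event hazard h in both arms, exponential time on treatment with median m (λ = ln 2/m), and the follow-up c at the data cut.

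**Full window, no cut.** P = 1 − e^(−hw) · λ/(λ + h), with h = 0.03:

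- m = 4: λ = 0.1733; P = 1 − 0.9061 × 0.8524 = 22.8%
- m = 8: λ = 0.0866; P = 1 − 0.9061 × 0.7428 = 32.7%

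**With a cut at c > w.** P = 1 − { e^(−hc − λ(c−w)) + e^(−hw) · λ/(λ + h) · [1 − e^(−(λ+h)(c−w))] }. At c = 12:

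- m = 4: 1 − (0.1541 + 0.7724 × 0.8299) = 20.5%
- m = 8: 1 − (0.3279 + 0.6731 × 0.6381) = 24.3%

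Equal hazard of 3% per month in every row (gaps from unrounded values; for uniform follow-up, P is averaged over c):

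| Follow-up at cut (assumed) | D, median 4 mo | ND, median 8 mo | Gap, points |
|---|---|---|---|
| 6 months, all | 15.1% | 15.7% | 0.7 |
| Uniform 3–15 months | 17.5% | 19.7% | 2.3 |
| Uniform 3–21 months | 19.0% | 22.6% | 3.6 |
| 12 months, all | 20.5% | 24.3% | 3.8 |
| 24 months, all | 22.6% | 30.6% | 8.0 |
| No cut | 22.8% | 32.7% | 9.9 |

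The first and last rows also show the second effect: a cut at 6 months takes D from 22.8% to 15.1% and ND from 32.7% to 15.7%.

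**Other assumptions.**

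- Higher hazard, 5% per month, no cut: 34.2% against 46.2%.
- Medians of 4 and 6 months, no cut, 3% per month: 22.8% against 28.1%. If ND is the arm with the 4-month median, it looks about 5 points safer.
- Front-loaded hazard (8% per month for 2 months, then 1%), medians 4 and 8, no cut: 20.5% against 24.6%, about 4 points. If all risk fell in the first 2 months and everyone was treated that long, the gap would be nil.

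**How often one trial would show it.** Simulation with 40 ND and 20 D, no cut, hazard set to give 20% in D: the ND percentage exceeds D in 76% of trials at medians 8 and 4, against 47% at equal medians.

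**What time-based measures give.** At h = 0.03 both arms have 3 first events per 100 person-months. Ignoring deaths, cumulative incidence is 1 − e^(−0.09) = 8.6% at 3 months and 1 − e^(−0.18) = 16.5% at 6 months in both arms, whatever the treatment durations.

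**The case against.** **The objective concerns the combination, not a difference.** Sizing is per arm, the toxicity stopping rule in Protocol 3.1.1.1 concerns ND alone, and no passage makes ND minus D a decision criterion. This stands. It limits the point to descriptive reading, but D is randomised and tabulated beside ND, so the informal comparison will be made. Precision is low: for 33% of 40 against 23% of 20 the 95% half-width is 1.96 × √(0.327 × 0.673/40 + 0.228 × 0.772/20), about 23 points.

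**A constant hazard may be wrong.** Protocol 4.1.1.2 reports that daratumumab infusion reactions fall mostly at the first infusion, and daratumumab dosing becomes less frequent over time (4.1.4.2). Early clustering shrinks the artefact. This stands, and it is why a range is given.

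**The analyses may already exist.** The Core Safety SAP may contain exposure-adjusted tables, and parts of Protocol Section 8 are redacted. A reader might infer that no time-at-risk analysis is planned anywhere. The documents do not support that. They show only that the endpoints as defined are crude and that the visible text adds nothing.

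**Early stopping of ND is not hidden.** A reader might infer that early ND stopping would pass for good tolerability. A subject who stops for a drug-related Grade 3-4 event already counts as an event, and discontinuations with reasons are summarised by arm (SAP 7.4.2), with AEs leading to discontinuation covered in 7.6.3.

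**Conclusion.** The point holds as one of interpretation. The window for the two primary AE endpoints can differ between ND and D, and in expectation the arm treated longer shows the higher percentage at equal monthly risk. With a 3% monthly hazard and medians of 4 and 8 months, the shift is about 1 to 4 points at 6 to 12 months of follow-up, about 8 at 24 months and 10 with no cut. Incomplete windows also lower both absolute rates.

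A reader might infer that ND will look 10 points more toxic. The documents do not support that: 10 points needs complete windows for everyone and a constant hazard, the documents do not say which arm will be treated longer, and a single trial of this size may not show the effect. Nor do they support discarding the crude percentages. This is a case for a supplementary analysis.

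**What to change.** Keep the crude percentages as primary. If the Core Safety SAP already provides the tables below, name them in the study SAP for these endpoints. Otherwise add, by arm, for drug-related Grade 3-4 AEs and separately for SAEs:

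- (a) The first-event rate per 100 person-months at risk, from first dose to the earliest of first event, death, 100 days after last dose or data cut, with an exact Poisson confidence interval.
- (b) Cumulative incidence at 3 and 6 months, with death as the competing event and censoring at 100 days after last dose or data cut. Stopping treatment must not be a competing event, since that would bring the exposure effect back.

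State that the censoring in (b) may be informative. Protocol 6.2.1 requires nonserious AE collection only to 100 days after last dose. Under medians of 4 and 8 months, 1 − e^(−λ(6 − 3.285)) gives 37.5% of D and 21% of ND reaching that limit before 6 months. Six months also exceeds the 3-month minimum follow-up, so the numbers at risk should be shown.

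Place both beside duration of therapy and use them to support the descriptive reading of ND next to D.

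Cost: SAP wording and a little programming from AE onset and dosing dates already collected. Limits: (a) assumes a constant rate, which (b) helps to check, and precision is limited with 40 and 20 subjects. No treatment rule changes.
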